4.3. Exclusion criteria

Current diagnoses of:

- a. Substance misuse (ICD10 F10—F19)
- b. Organic brain syndrome (ICD10 F00—F09)
- c. Adult personality disorder (ICD10 F60—F69)
- d. Pervasive developmental disorder (ICD10 F84)
- e. Schizophrenia (ICD10 F20-F29)
- f. Bipolar disorder (ICD 10 F30-31)
- g. Contraindications to neurosurgery
- h. Pregnancy

5. Study Design

See Figure 1

5.1. The study design will allow assessment of DBS at each of the two sites counterbalancing for order. Stimulation at both sites will not be included in the randomisation of order and will always occur last because:

- a. The optimal stimulation parameters for each target alone will have already been identified for each individual and thus the optimum parameters in combination will be determined more quickly; *and*
- b. We are predicting that stimulation of both sites will be the most efficacious condition and that withdrawal of effective therapy would risk higher rates of patient drop-out from the blinded evaluation and could be regarded as unethical.

5.2. We have opted not to have a wash-out period between the three DBS phases because:

- a. Patients may not wish to have the DBS switched off if they have experienced symptom reduction by the previous DBS settings and this will risk higher rates of

patient drop-out from the blinded evaluation; this has been experienced in one previous study⁸.

- b. The purpose of the study is to compare DBS at two sites both individually and together to establish the best site(s) for UK practice in the future - it is not to establish absolute efficacy at each site (which would require both on and off DBS phases) as this has been adequately demonstrated previously.

5.3. A potential criticism is that there may be a carry-over effect from previous stimulation parameters when patients are switched from the first site to the second site which will affect the assessments (*see Figure 1*). Evidence about how long stimulation effects continue to affect OCD behaviour following cessation comes from two studies of STN DBS in which sham and active stimulation were compared ^{8, 9}. During a 2 or 4 week wash-out periods the patients switching from active to sham stimulation had reverted to their baseline symptom severity by the end of these periods. This suggests that the effect of 12 weeks of active stimulation at the second site will not reflect carry-over effects. In addition because we are counterbalancing for order, the presence of any carry-over effect can be examined at the end of the study.

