- 1.3. Before DBS for OCD can be introduced into routine clinical practice, further research is required to determine the optimum DBS brain target. It may also be possible to improve upon the degree of response to DBS by understanding more about the mechanisms of action at the two target sites - although two-thirds were considered responders in previous studies, the patients remained symptomatic, being reduced from the 'extreme/severe' to the 'moderate' category ⁷. Furthermore, although CBT will not have previously been effective in these patients, DBS may reduce symptoms enough to enable them to use CBT more effectively and, indeed, the combination may result in a better outcome than DBS alone. To address these questions we have brought together a network of specialist OCD clinicians, leading OCD cognitive neuroscientists and expert DBS clinicians to undertake the first UK study of DBS for severe, medically intractable OCD.

2. Aims and Hypothesis

2.1. The overarching aim is to compare the effects of VC/VS and STN DBS in the same patients. We will test the hypothesis, grounded in cognitive neuroscience, that DBS at both sites is better than either site alone for treating the symptom dimensions of OCD. Specifically, we will employ novel cognitive paradigms and neurophysiological measures of cortical synaptic function to test the hypothesis that VS/VC and STN DBS have different mechanisms of action and that alleviation of OCD symptoms is mediated by improvement in mood/anxiety with VS/VC DBS and by directly interrupting obsessions and compulsions with STN DBS. We will additionally determine whether adjunctive CBT enhances the response to DBS by providing the cognitive and behavioural skills to optimise symptom management and daily function.

3. Scientific Rationale

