- 3.7.** OCD symptoms and cognitive impairment may be mediated by abnormal cortical excitability due to aberrant long term depression (LTD) synaptic plasticity¹⁸ and/or reduced GABA-mediated intracortical inhibition¹⁹. Transcranial magnetic stimulation (TMS) can be used to measure these neurophysiological processes safely in patients undergoing DBS and both abnormalities have been shown to normalise following DBS in other disorders²⁰. We will use TMS to assess these neural processes before and after DBS in OCD patients and test for whether there are differential changes from the two DBS sites and whether combined VS/VC and STN DBS produces more vigorous improvements compatible with our hypothesis concerning the superior clinical effects of this condition. We will measure intracortical inhibition not only at rest but also during the anticipation of reinforcement, previously shown to affect motor cortex excitability²¹ and which we predict will be specifically affected by VS/VC DBS.

4. Research Programme

- 4.1. Subjects:** Six patients will be recruited from the OCD National Specialist Commissioned Services of [name], South West London and St George's Mental Health Trust (SWLSG MHT) and [name], Herts Partnership NHS Foundation Trust (HPFT).
- 4.2. Inclusion criteria:** The inclusion criteria have been designed to be consistent with previous OCD DBS studies and to ensure that patients have not responded in a useful and sustained manner to either modifications of medication or any form of CBT⁴.

Patients must have undergone intensive treatment and have demonstrable treatment resistance as defined by:

- a. At least two SRIs for a minimum of 12 weeks at optimal British National Formulary (BNF) doses.
- b. Augmentation of SRI treatment with antipsychotic drugs administered at maximally tolerated doses or by extending the SSRI dose beyond BNF limits.
- c. Two trials of CBT of at least 10 hours.
- d. Failed inpatient treatment for OCD.

Patients must also satisfy the following criteria:

- e. Age > 20 years.

- f. Confirmation of a primary diagnosis of obsessive compulsive disorder (ICD10 F42.0—F42.9).
- g. Duration of illness of at least 10 years.
- h. At least 2 years of unremitting symptoms despite intensive psychopharmacological and psychological treatment or failure to sustain, over a 3 month period, a response to inpatient psychological treatment by at least 33% with accompanying optimised pharmacological therapy.

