5.4. Stages

Stage 1a: Consistent with the existing nationally commissioned clinical pathway, all potential participants will be offered the choice of anterior cingulotomy or DBS. Although this study is designed to examine the effect of DBS and not to compare the two procedures, adopting the standard care pathway will ensure that existing robust governance and consent procedures will be applied for all participants. Potential patients will be identified from the clinical case loads of [name] and [name]. Their clinical files will be reviewed by their OCD specialist consultant, [name] or [name], and [name] to establish that they fulfil the inclusion/exclusion criteria. [name] directs the OCD national specialist commissioned service for ablative neurosurgery at Ninewells Hospital, Dundee, and will ensure that the patients meet the criteria for suitability for anterior cingulotomy ⁴. The OCD clinicians will discuss both procedures (anterior cingulotomy and DBS) with each patient and establish that they are able to provide written informed consent.

Stage 1b: A separate group of up to 20 patients will be identified for the purpose of undergoing all neuropsychological, neurophysiological and clinical assessments as are proposed for the group of patients being offered DBS. This group of patients will be identified through the same pathways. Same inclusion and exclusion criteria set for this trial will be applied to identify these patients. This group of patients will differ from the DBS group in the following aspects:

- a) They are still being offered standard treatment of their refractory OCD in a specialist OCD Service.
- b) They are not being offered DBS or neurosurgery.

All assessments will be performed on this group of patients at exactly the same intervals as those proposed for the patients undergoing DBS. Assessment data obtained from this group of patients will help us to improve the accuracy of the results obtained from the main trial by facilitating the identification of neuropsychological, neurophysiological and/or clinical changes specific to DBS.

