6.1. Medication: Patients are likely to be taking a combination of high dose SRIs and antipsychotic medication. This medication will be kept constant throughout the study except for the preoperative period. Evidence suggests that patients taking SRIs are at increased risk of bleeding because of a non-dose dependent reduction in platelet serotonin²³. To decrease this risk, patients will be withdrawn from SRIs and be free of this medication for 10 days prior to surgery to allow platelets to be replaced. Medication will be reinstated during the post-operative period.

6.2. DBS Neurosurgery: All patients will undergo implantation of bilateral electrodes at both the VS/VC and STN sites under general anaesthesia. On each side, the two electrodes (STN and VC/VS) will be implanted through a single burr hole. A high-resolution MRI scan will be used to calculate target coordinates for each patient. An MRI will also be performed to verify accurate electrode location²⁴ immediately following surgery. Both scans will be performed under general anaesthesia. Each STN electrode will have 4 electrical contacts at its distal tip (with a 0.5mm separation) to allow fine tuning of the exact site for stimulation delivery. Each VS/VC electrode will have 4 electrical contacts at its distal tip (with a 1.5mm separation) to allow fine tuning of the exact site for stimulation delivery. Two non-rechargeable batteries (Activa PC) will be connected to the electrodes and positioned under the skin of the right and left chest wall so that they correspond to the same set of

electrodes for each patient: one for the 2 STN electrodes and one for the 2 VC/VS electrodes.

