6.4. DBS stimulus adjustment and blinding: Two neurologists making the DBS adjustments ([name] and [name]) will allocate 3 patients to receive STN DBS initially and 3 to VC/VS DBS. All other team members and the patient will be blind to the allocation. Each electrode has 4 electrical contacts at its distal tip (with a 0.5mm separation) to allow fine tuning of the exact site for stimulation delivery. The optimal DBS parameters will be derived in an iterative fashion over a period lasting up to 2 weeks at the start of each 12 week stimulation block. This will require the patient to visit the DBS unit on a daily basis. At the outset, each contact will be screened with voltages up to 4V (STN electrodes) or 8V (VC/VS electrodes) using monopolar stimulation and a pulse width of 60us, and frequency of 130Hz. Note will be made of the immediate clinical effects from stimulation delivered through each contact in turn, and the threshold associated with positive and negative effects. Expected acute adverse effects of stimulation include transient sadness, anxiety, euphoria, giddiness or hypomania ^{7, 9}. These will be monitored and documented with the use of visual analogue rating scales which rate subjective feelings ²⁴. Stimulation will be adjusted to avoid any sustained negative physical or psychiatric symptoms. In the absence of any acute clinical effects, the post-operative imaging will be used to select the contact closest to the planned target. The initial optimal stimulation parameters will be refined according to patient feedback as often as necessary over the first 2 weeks, including possible use of stimulation through multiple contacts per electrode or using a bipolar configuration. These parameters will then be kept constant through the remainder of each 12 week block with further adjustment performed only in the event of delayed physical or psychiatric adverse events, considered by the trial team to be directly attributable to the stimulation.

6.5. Clinical assessments: OCD and co-morbid disorders will be assessed using The Mini International Neuropsychiatric Inventory (MINI) ²⁶ as part of the assessment of inclusion/exclusion criteria. In addition, Young Schema Questionnaire (YSQ) ⁴⁹ will be used to identify comorbid Personality Traits. Regular clinical assessments of the strength and

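### Combined stimulation is always the third block, so the plan cannot separate its effect from time and carry-over, and the four-condition Friedman test does not test whether both sites beat either alone

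*Protocol*

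**What the plan says.** Section 2.1 of the protocol states the hypothesis that "DBS at both sites is better than either site alone for treating the symptom dimensions of OCD", and section 3.4 repeats the prediction. Section 4.1 sets the size: "Six patients will be recruited".

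Section 5.1 fixes the place of the combined condition: "Stimulation at both sites will not be included in the randomisation of order and will always occur last". It gives two reasons. The best settings for each target will already be known by then, and, because the team expects combined to work best, "withdrawal of effective therapy would risk higher rates of patient drop-out from the blinded evaluation and could be regarded as unethical". Section 5.4, Stages 6 to 8, sets three blocks of 12 weeks with 24 hours off between them, and 5.2 declines a wash-out.

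Section 6.4 says that the two adjusting neurologists "will allocate 3 patients to receive STN DBS initially and 3 to VC/VS DBS". It continues: "All other team members and the patient will be blind to the allocation". Section 5.3 relies on the counterbalancing to examine carry-over, and speaks of the switch from the first site to the second.

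Section 7.2 plans one Friedman test on YBOCS over four conditions: pre-operative baseline, STN, VC/VS and combined. The only pairwise comparison it names between DBS conditions is VC/VS versus STN, on responder status (McNemar). Section 5.4, Stage 1b, adds up to 20 patients without DBS: "All assessments will be performed on this group of patients at exactly the same intervals as those proposed for the patients undergoing DBS". Section 7 does not mention them.

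**The concern.** The order of the two single sites is balanced, but the combined condition has no counterpart at any other position. If patients improve over the study for any reason other than having two active sites (passage of time, accumulated stimulation, effects carried over from earlier blocks, or the expectation that the last block is best), that improvement appears as an advantage of combined stimulation. The protocol justifies the order but does not say what it costs the inference, and 7.2 does not carry that cost into the analysis.

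Two stated purposes are at stake. Section 5.2 wants the best site or sites for future UK practice, and 7.3 wants an effect estimate to size a later trial. A finding that combined is best, taken at face value, would feed into both.

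**Working it through.** The protocol gives no power, effect size, SD or drift, so there is no planned figure to reproduce. Drift and SD below are assumptions. Y1, Y2 and Y3 are a patient's YBOCS scores at the end of blocks 1 to 3.

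**1. Timing.** Inputs: at least 4 weeks off after discharge (Stage 5), three blocks of 12 weeks (Stages 6 to 8), and up to 2 weeks of tuning per block. Stage 6 puts tuning outside the 12 weeks; 6.4 can be read as putting it inside. The 24-hour gaps are ignored.

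- Tuning inside: blocks end at weeks 16, 28 and 40. Combined minus mean single = 40 − (16 + 28)/2 = 18 weeks.
- Tuning outside: blocks end at weeks 18, 32 and 46. 46 − (18 + 32)/2 = 21 weeks.
- Mean block position: STN 1.5, VC/VS 1.5, combined 3.0.

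**2. Bias from linear drift of x points per block.**

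- Combined versus mean single: 3x − 1.5x = 1.5x. With x = 1, 2, 3, 4 the spurious advantage is 1.5, 3.0, 4.5 and 6.0 points.
- STN versus VC/VS: 1.5x − 1.5x = 0.

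**3. What the planned test shows.** Simulation of six patients in the stated order, with a common 12-point DBS effect, no drift and no difference between the three DBS conditions: the four-condition Friedman test at the 5% level rejects in 97% of runs (SD 4 per measurement) or 74% (SD 6). A significant result can thus come from baseline versus DBS alone.

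**4. How drift looks when there is no true difference between DBS conditions** (40,000 runs per setting).

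| Drift per block | Combined has best mean, SD 4 / SD 6 | Friedman on the three DBS conditions rejects, SD 4 / SD 6 |
|---|---|---|
| 0 | 33% / 33% | 3% / 3% |
| 2 | 83% / 70% | 10% / 6% |
| 3 | 95% / 84% | 19% / 10% |

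For a direct contrast, take a paired t-test of Y3 against (Y1 + Y2)/2, one-sided 2.5%. The standard error is SD × √(1.5/6): 1.5 points for SD 3 and 2.5 points for SD 5. With x = 2 the bias is 3.0 points and false superiority is about 37% (SD 3) or 16% (SD 5). With x = 3 the bias is 4.5 points and the rates are about 67% and 31%. The protocol does not plan this test, so these rates are illustrations only.

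**5. Reach of the carry-over check.** Counterbalancing compares 3 with 3 patients in blocks 1 and 2 and says nothing about block 3. Even there, the smallest two-sided exact rank-sum p-value is 2/20 = 0.10.

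**6. Can the six patients correct it?** Let s, v and c be the STN, VC/VS and combined effects. In Y3 − 2·Y2 + Y1 the linear drift term is 3x − 4x + x = 0. STN-first patients give c − 2v + s and VC/VS-first patients give c − 2s + v; averaged 3:3 this is c − (s + v)/2, the wanted contrast. Its variance is (1 + 4 + 1)·SD² = 6·SD² against 1.5·SD² for the raw contrast, so the standard error doubles. It fails if improvement levels off. With 4 points gained between blocks 1 and 2 and none after, the raw contrast is biased by 4 − (0 + 4)/2 = +2 in favour of combined, and the adjusted one by 4 − 8 + 0 = −4.

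**The case against.** The strongest defence is that the fixed order is disclosed and reasoned, and that the study is a six-patient pilot that begins with description and feeds a later trial. Section 5.3 also cites evidence that symptoms returned to baseline within wash-outs of 2 or 4 weeks; if that holds for block 3, stimulation carry-over after 12 weeks should be small. Stage 1b provides a concurrent group. Details of contrasts often sit in a statistical analysis plan, which is not shown.

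Much of this stands. The order is a defensible choice and is not criticised here. The wash-out evidence bears on carry-over but not on time trend, accumulated benefit or expectation. Stage 1b could show a background trend, but it is not randomised and has no DBS. What remains is that the protocol itself fixes a test that does not match its own hypothesis.

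Some stronger readings are tempting and are not supported:

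- A reader might infer that block 3 is openly known to all. Section 6.4 states blinding and 5.1 speaks of a blinded evaluation. That block 3 can be deduced is a strong inference: its content is fixed and Stage 2 has the protocol explained to patients in detail. Masking raters to visit is neither described nor excluded.
- A reader might blame re-established SRI treatment for drift. Section 6.1 says "Medication will be reinstated during the post-operative period" and otherwise keeps medication constant. Block 1 ends at about week 16 to 18 after discharge, already beyond the 12 weeks that 4.2 uses for an SRI trial, so this explanation largely falls away.
- A reader might take the 37% or 67% as error rates of the planned analysis. They depend on an assumed drift, for which the protocol gives no evidence, and on a test it does not plan.
- A reader might treat Y3 − 2·Y2 + Y1 as a cure, or allow a superiority claim whenever it agrees in direction with the raw contrast. Under that rule false superiority is still about 24% (x = 2) or 39% (x = 3) at SD 3.

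**Conclusion.** The point holds as a limit on what the trial can conclude. Combined versus single is completely confounded with block 3 in the six DBS patients, the concealment does not reliably reach it, and a significant four-condition Friedman test would not show that both sites beat either alone. The 18 to 21 week gap follows from the stated schedule. The bias of 1.5x follows from the order and assumes linear drift; the size of x is unknown. Data from these six patients cannot remove an arbitrary block-3 effect, only a linear drift, and then only without carry-over.

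STN versus VC/VS is not affected in this way: it is counterbalanced, concealed and free of bias from linear drift, though unequal carry-over between the sites could still distort it.

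**What to change.** Keep the treatment order and change sections 2.1 and 7.2.

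- **(a) Inference.** State that the counterbalanced, blinded STN versus VC/VS comparison carries the inference. Label combined versus single as exploratory, order-confounded and not reliably blinded, and state that superiority of combined stimulation will not be concluded from the Friedman result.
- **(b) Stage 1b.** Report the Stage 1b YBOCS change over the same intervals beside the combined-versus-single contrast, noting that this group is non-randomised and cannot capture DBS carry-over or expectation.
- **(c) Optional sensitivity estimate.** Report the patient mean of Y3 − 2·Y2 + Y1, stated to be valid only under linear drift and no carry-over and to have twice the standard error of the raw contrast. It should be neither a correction nor a condition for claiming superiority.

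The cost is protocol wording and a few summaries from assessments already planned. No treatment, visit or patient number changes. The downside is a weaker claim for combined stimulation, which is all the design can support.

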5.4. Stages

Stage 1a: Consistent with the existing nationally commissioned clinical pathway, all potential participants will be offered the choice of anterior cingulotomy or DBS. Although this study is designed to examine the effect of DBS and not to compare the two procedures, adopting the standard care pathway will ensure that existing robust governance and consent procedures will be applied for all participants. Potential patients will be identified from the clinical case loads of [name] and [name]. Their clinical files will be reviewed by their OCD specialist consultant, [name] or [name], and [name] to establish that they fulfil the inclusion/exclusion criteria. [name] directs the OCD national specialist commissioned service for ablative neurosurgery at Ninewells Hospital, Dundee, and will ensure that the patients meet the criteria for suitability for anterior cingulotomy ⁴. The OCD clinicians will discuss both procedures (anterior cingulotomy and DBS) with each patient and establish that they are able to provide written informed consent.

Stage 1b: A separate group of up to 20 patients will be identified for the purpose of undergoing all neuropsychological, neurophysiological and clinical assessments as are proposed for the group of patients being offered DBS. This group of patients will be identified through the same pathways. Same inclusion and exclusion criteria set for this trial will be applied to identify these patients. This group of patients will differ from the DBS group in the following aspects:

- a) They are still being offered standard treatment of their refractory OCD in a specialist OCD Service.
- b) They are not being offered DBS or neurosurgery.

All assessments will be performed on this group of patients at exactly the same intervals as those proposed for the patients undergoing DBS. Assessment data obtained from this group of patients will help us to improve the accuracy of the results obtained from the main trial by facilitating the identification of neuropsychological, neurophysiological and/or clinical changes specific to DBS.

Stage 2: Patients who opt for DBS will be referred to the NHNN. At this visit the research protocol will be explained in detail to them. They will be offered the opportunity to visit the ward prior to admission. They will be seen in the multidisciplinary DBS clinic at the NHNN where they will be assessed for suitability for the surgery. Ability to provide written informed consent will be re-assessed at this stage thereby establishing consistency. Written informed consent will be taken at this stage if the patient is ready to decide. If the patient would like more time, written informed consent will be obtained at subsequent clinic appointments with [name] or [name].

Stage 3: Prior to surgery any serotonin reuptake inhibitor (SRI) medication will be withdrawn and they will remain free of this medication for the 10 days before surgery (see below). A time period of 7-21 days will be allowed for the careful down-titration of medication during the withdrawal process. The actual duration of withdrawal will be informed by decided by taking clinical and historical factors into account on a case-by-case basis. The participant might require an inpatient admission during the process of withdrawal from medication and a provision will be made for the same. We wish to undertake all assessments when patients are taking their routine medication. If they are taking SRIs we will undertake initial assessments at a separate visit to the hospital prior to admission for surgery and before their medication is withdrawn.

Stage 4: Patients will be admitted for DBS neurosurgery to a dedicated neuropsychiatry ward (Hughlings Jackson) at the NHNN. It is anticipated that they will stay for up to 14 nights, depending on whether the initial assessments have already been completed or not, and to allow post-operative recovery and the removal of the stitches by the surgical team 10 days after surgery.

Stage 5: Following discharge, stimulation will remain off for a minimum of 4 weeks to allow the mechanical effect of post-surgical oedema to resolve. This period can be extended, if necessitated by clinical reasons.

Stage 6: Randomisation and initiation of STN or VS/VC DBS for 12 weeks. The stimulation parameters will be adjusted on a daily basis until judged optimal (see below for details). Optimisation process will also be guided by a modified Visual Analogue Scale (VAS) to measure urges to perform compulsions and fluctuations in the mood. Specific behavioural challenges will be designed for each patient in accordance with their previous clinically documented symptoms of OCD and will be administered by the research psychiatrist during the optimisation process to elicit obsessive and compulsive responses. The strength and

intensity of these responses will be measured with modified Visual Analogue Scales by both patient and the psychiatrist. This may take up to 2 weeks; patients will have the option of being admitted to Hughlings Jackson ward or attending as a day case. If the latter, they may stay overnight at a local hotel with a carer (according to standard NHHN day unit procedures) or stay overnight at home if practical. Stimulation optimisation period will not be included in the 12 weeks allocated to the stimulation stage.

Stage 7: The current stimulation will be switched off for 24 hours and the alternative site stimulated for 12 weeks. The same procedures and options for hospital attendance in Stage 6 will apply.

Stage 8: The current stimulation will be switched off for 24 hours and both sites will be stimulated for 12 weeks. The same procedures and options for attendance in Stage 6 and 7 will apply.

Stage 9: Patients will continue with DBS at their best DBS site(s) and settings. This may require a further admission for stimulus/site adjustment as above if the current stimulation is not judged to be optimal.

Stage 10: After 12 weeks stabilisation on the best DBS settings and site, patients will be offered inpatient cognitive behavioural therapy at SWLSG MHT for 12 weeks.

6. Study procedures and assessments

6.1. Medication: Patients are likely to be taking a combination of high dose SRIs and antipsychotic medication. This medication will be kept constant throughout the study except for the preoperative period. Evidence suggests that patients taking SRIs are at increased risk of bleeding because of a non-dose dependent reduction in platelet serotonin²³. To decrease this risk, patients will be withdrawn from SRIs and be free of this medication for 10 days prior to surgery to allow platelets to be replaced. Medication will be reinstated during the post-operative period.

6.2. DBS Neurosurgery: All patients will undergo implantation of bilateral electrodes at both the VS/VC and STN sites under general anaesthesia. On each side, the two electrodes (STN and VC/VS) will be implanted through a single burr hole. A high-resolution MRI scan will be used to calculate target coordinates for each patient. An MRI will also be performed to verify accurate electrode location²⁴ immediately following surgery. Both scans will be performed under general anaesthesia. Each STN electrode will have 4 electrical contacts at its distal tip (with a 0.5mm separation) to allow fine tuning of the exact site for stimulation delivery. Each VS/VC electrode will have 4 electrical contacts at its distal tip (with a 1.5mm separation) to allow fine tuning of the exact site for stimulation delivery. Two non-rechargeable batteries (Activa PC) will be connected to the electrodes and positioned under the skin of the right and left chest wall so that they correspond to the same set of

electrodes for each patient: one for the 2 STN electrodes and one for the 2 VC/VS electrodes.

6.3. Magnetic Resonance Imaging: Routine pre- and post-operative MR images will be obtained from a single 1.5T MRI scanner (Siemens, Erlangen, Germany) using a head transmit/receive coil that does not extend over the chest to avoid RF exposure to areas outside the head and hence to minimize the area of the DBS circuit exposed. The MRI acquisition protocol is specifically designed to prevent the scanner-predicted head-average specific absorption rate (SAR) exceeding 0.4 W/kg while still providing adequate visualization of the target anatomy. The gradient slew rate (dB/dt) will be less than 20 T/s for all acquisitions. These MRIs will be when the patients are under general anaesthesia. On the day before surgery, patients will be invited to undergo a 3T diffusion tensor MRI scan when awake. This is not routine and is part of the research study; it will enable us to perform white matter tractography and identify the white matter output tracts and distal projection sites for each electrode.

6.4. DBS stimulus adjustment and blinding: Two neurologists making the DBS adjustments ([name] and [name]) will allocate 3 patients to receive STN DBS initially and 3 to VC/VS DBS. All other team members and the patient will be blind to the allocation. Each electrode has 4 electrical contacts at its distal tip (with a 0.5mm separation) to allow fine tuning of the exact site for stimulation delivery. The optimal DBS parameters will be derived in an iterative fashion over a period lasting up to 2 weeks at the start of each 12 week stimulation block. This will require the patient to visit the DBS unit on a daily basis. At the outset, each contact will be screened with voltages up to 4V (STN electrodes) or 8V (VC/VS electrodes) using monopolar stimulation and a pulse width of 60us, and frequency of 130Hz. Note will be made of the immediate clinical effects from stimulation delivered through each contact in turn, and the threshold associated with positive and negative effects. Expected acute adverse effects of stimulation include transient sadness, anxiety, euphoria, giddiness or hypomania ^{7, 9}. These will be monitored and documented with the use of visual analogue rating scales which rate subjective feelings ²⁴. Stimulation will be adjusted to avoid any sustained negative physical or psychiatric symptoms. In the absence of any acute clinical effects, the post-operative imaging will be used to select the contact closest to the planned target. The initial optimal stimulation parameters will be refined according to patient feedback as often as necessary over the first 2 weeks, including possible use of stimulation through multiple contacts per electrode or using a bipolar configuration. These parameters will then be kept constant through the remainder of each 12 week block with further adjustment performed only in the event of delayed physical or psychiatric adverse events, considered by the trial team to be directly attributable to the stimulation.

6.5. Clinical assessments: OCD and co-morbid disorders will be assessed using The Mini International Neuropsychiatric Inventory (MINI) ²⁶ as part of the assessment of inclusion/exclusion criteria. In addition, Young Schema Questionnaire (YSQ) ⁴⁹ will be used to identify comorbid Personality Traits. Regular clinical assessments of the strength and

intensity of obsessive and compulsive symptoms will be made on Visual Analogue Scale (VAS) by using appropriate behavioural challenges, which will be designed specifically for each patient. Urge to perform compulsions will be monitored and quantified using similar VAS at each assessment point. The effect of DBS on OCD, affective symptoms, social function and quality of life will be assessed with the following validated scales:

OCD symptoms:

- a. Yale-Brown Obsessive Compulsive Scale Symptoms checklist (YBOCS-I) ²²
- b. Yale-Brown Obsessive Compulsive Scale (Version-II) ⁴⁷

Affective symptoms:

- c. Montgomery Asberg Depression Rating Scale (MADRS) ²⁷
- d. Beck Depression Inventory – Version 2 (BDI-II) ²⁸
- e. Young Mania Scale (YMS) ²⁹
- f. Barrett Impulsiveness Scale (BIS) ³⁰

Comorbid Tics:

- g. Yale Global Tic Severity Scale (YGTSS) ⁴⁸

Anxiety:

- h. Hamilton Anxiety Scale (HAS) ³¹
- i. Beck Anxiety Inventory (BAI) ³²

Social Function:

- j. DSM IV General Assessment of Function scale (GAF)
- k. Sheehan Disability Scale (SDS) ³³
- l. Cognitive Assessment Instrument of Obsessions and Compulsions (CAIOC-13) ³⁴

Subjective wellbeing:

- m. SF-36 ³⁵ (quality of life scale)

6.6. Cognitive assessments:

Years spent in education will be noted for all patients before they undergo the tests for general cognitive function.

General cognitive function:

- a. The National Adult Reading Test ³⁶
- b. CANTAB Paired Associate Learning Task (PAL) ³⁷
- c. Verbal Fluency ³⁸

Reinforcement learning and emotional processing:

- d. The probabilistic learning and reversal task ³⁹
- e. CANTAB Affective Go/No Go ³⁶

f. **CANTAB Reward Sensitivity Test**

Executive control:

- g. CANTAB Stop Signal Reaction Time Task ³⁶
- h. CANTAB ID/ED Task ³⁶

The rationale for using these tests is that both stop-signal inhibition and extra-dimensional set-shifting have been shown to be sensitive to OCD (as well as in their first degree relatives) ¹⁷. Performance in both tasks is mediated by circuits including the inferior frontal cortex and orbitofrontal cortex ^{10,40}. Our hypothesis predicts that the SSRT and ID/ED will be more sensitive to changes induced by STN DBS. Preliminary work indicates that OCD patients with high YBOCS scores may be impaired in probabilistic reinforcement learning (70/30%); the Affective Go/No Go tests attentional biases in mood states. Our hypothesis predicts that these two tests will be more sensitive to changes induced by VC/VS DBS. Paired associate learning has also been shown to be deficient in OCD ⁴¹, although the precise neural substrates for this deficit are not known. Mild word finding difficulty and forgetfulness have been reported following DBS in several disorders and will be assessed with verbal fluency and PAL. This battery of tests will take approximately 1 hour to administer.

